- **13. Costs to the Subject:** No additional costs to the patient will be incurred as a result of this add-on research protocol. The participant will receive UGX 15000 as stipend for participating in the study.
- **14. Statistical Considerations:** Objectives: The primary objective of this study is to estimate the test characteristics (sensitivity, specificity, and the false positive and false negative rates) of the portable NIR-based device (InfraScanner 2000TM) in the identification of any size hematoma among patients hospitalized at MRRH who have sustained or who are suspected to have sustained head trauma. For those who go on to obtain CT scans, the results of the CT scan(s) will serve as the gold standard. The sensitivity, specificity, and the false positive and false negative rates will be estimated at the patient level and at the scan level. Approximately 10% of patients are anticipated to have more than one CT scan.

A secondary objective is to estimate the test characteristics of the InfraScanner 2000TM in identification of hematomas within its detection limits (volume >3.5 mL and depth <2.5 cm) compared to CT scan results as the gold standard.

Exploratory objectives include:

- 1. Examining the impact of factors such as hematoma type, location, and patient age on test characteristics of the InfraScanner 2000TM
- 2. Determining the minimum resolution detectable by the InfraScanner 2000TM
- 3. Analyzing the effects of extracranial hematomas, lacerations, and swelling on the performance characteristics of the device
- 4. Estimating Receiver Operating Characteristic (ROC) curves with patient and scan as the units of analysis (20).

Study Design:

a) Eligibility: All patiets with suspected TBI and meet the WHO and Brain Injury (BI) trust criteria for CT scaning

Inclusion criteria

Patients with suspected TBI above 12 years with suspected TBI and meet the BI criteria for CT scan

Patients that present with CT that was taken within 30 minutes

Patients with TBI that occurred more than 48 hours

Patietns with suspected TBI who present to Mayanja Memorial Hospital for CT scan but managed at Mbarara Regional Referral Hospital

Patients who do not present with CT scan images and cannot afford to pay for a CT Scan, will be included in the study and the study team will pay for their scans.

Exclusion Criteria

Infrascanner Study PI: [name]

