Patients who present died Patients with images other than Mayanja Memorial Hospital and Mbarara Regional Referral Hospital

b) Standard of comparison:

All patients entered into the trial will undergo at least one cranial scanning using the InfraScanner 2000TM at the time of presentation. For patients who go on to get a CT scan, they will be scanned using the InfraScanner 2000TM within 30 minutes of each subsequent CT. Patients and care providers will be blinded to the results of InfraScanner 2000TM. The standard for comparison will be determined as follows. A CT result that is positive for hematoma will be considered a true positive and a CT result that is negative for hematoma will be considered a true negative. For patients who never go on to obtain a CT scan, their InfraScanner 2000TM results will be analyzed in the context of clinical data.

Definitions of Sensitivity, Specificity, False Positive, False Negative: Let A^+ denote the event that the test is positive for hematoma and B^+ denote the event that a hematoma is present. Sensitivity, $P(A^+/B^+)$, will be defined for each patient (scan) as the probability that a true hematoma as determined by CT scan will be detected (21). Similarly, let A^- denote the event that the test is negative for hematoma and B^- denote the event that a hematoma is not present. Specificity, $P(A^-/B^-)$, will be defined as the probability of being negative for hematoma on the InfraScanner 2000TM scan within 30 minutes of CT given the patient has no hematoma present.

The false positive rate will be defined as $P_{F^+} = P(B^-/A^+) = P(A^+/B^-)[1-P(B^+)]/P(A^+)$. Similarly, the false negative rate will be defined as $P_{F^-} = P(B^+/A^-) = [1-P(A^+/B^+)]P(B^+)/[1-P(A^+)]$. Estimates for the false positive and false negative rates will be provided for a range of values for the prevalence of hematomas.

c) Sample Size

Computation of the required number of patients is based on estimating the sensitivity of each method to within at most \pm 0.10 with 90% confidence. The 90% confidence interval for the sensitivity is given by $P_{Sens} \pm$ 1.645*SE(P_{Sens}) where SE(P_{Sens})= [(P_{Sens})(1- P_{Sens})/N; N denotes the number of true positives.

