With 68 patients with positive findings of hematoma (i.e. CT-proven SDH/EDH) sensitivity can be estimated to within at most +/- 0.099 with 90% confidence. Assuming 20% of patients have true hematomas detected, 340 patients who obtain CT scans must be accrued (10). We estimate that 50% of patients will obtain CT scans. Accounting for this, and allowing for a 5% dropout rate the required sample size for this trial is 720 total participants. With 272 patients having negative findings for hematoma via CT, specificity can be estimated to within at most +/- 0.05 with 90% confidence.

d) Interim Analysis

Infrascanner Study PI: [name]

An interim analysis will be conducted once 150 patients with accompanying CT scans have been enrolled in the study to estimate the prevalence of hematomas at MRRH. The adjusted 90% confidence interval estimate for sensitivity will also be constructed. Based on these results the trial may be amended to enroll fewer or more patients.

e) Accrual

It is anticipated that at least 120 patients per month will be accrued and studied at MRRH. Study enrollment should thus be completed within approximately 6 months. The collection period for each research participants concludes within 30-days while in hospital following his or her initial consent, patient or surrogate/patient attendant decision to withdraw from further participation, or hospital discharge, or patient death; whichever occurs first.

15. Data and Safety Monitoring: Patients will be under continuous supervision during the entirety of each data collection period. Outside the ~10-minute window of each collection period, the patient is not subjected to any research intervention or influenced by the research in any way. As part of their treatment, patients will be under hospital care for their diagnoses for which they were admitted, and the research team will be in continual contact with the team regarding their clinical status and enrollment in the study.

The PI will be responsible for securing and monitoring the data, including a quarterly review of data storage procedures.

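### Accuracy is stated for all hospitalised head-trauma patients but can be estimated only in the half expected to have CT, and the plan gives no method for the other half

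*Combined protocol and SAP*

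**What the plan says.** All references are to the combined protocol and SAP.

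- **Section 14, Objectives.** Sensitivity, specificity and the false positive and false negative rates are to be estimated "among patients hospitalized at MRRH who have sustained or who are suspected to have sustained head trauma". The reference standard is conditional: "For those who go on to obtain CT scans, the results of the CT scan(s) will serve as the gold standard".
- **Section 14(b), Standard of comparison.** Sensitivity is defined against hematoma as shown by CT, and specificity on the device scan done close to CT. For everyone else the whole provision is "For patients who never go on to obtain a CT scan, their InfraScanner 2000TM results will be analyzed in the context of clinical data". Patients and care providers are blinded to the device result; Section 12 also blinds treating physicians. The false positive and false negative rates are defined as the complements of PPV and NPV and are to be tabulated over several assumed prevalences.
- **Section 14(c), Sample Size.** "Assuming 20% of patients have true hematomas detected, 340 patients who obtain CT scans must be accrued". Then: "We estimate that 50% of patients will obtain CT scans".
- **Section 14(d), Interim Analysis.** After 150 patients with CT, an analysis is made "to estimate the prevalence of hematomas at MRRH", and enrolment may be changed.
- **Section 14(a), Eligibility.** Patients must meet criteria for CT, and the study pays for CT for those who arrive without images and cannot afford a scan.
- **Section 17, Limitations.** Only brain swelling and contusions are mentioned. Missing CT verification is not.

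**The concern.** The population named in the objective is about twice the population in which the truth will be known. CT-only estimates carry over to the whole only if CT uptake is unrelated to the factors that determine hematoma presence and device accuracy, and the plan neither argues nor checks this.

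There are plausible ways for it to fail. Severity, early death, cost and access can each decide who is scanned. Section 3 reports that the device's sensitivity in the team's earlier series was 86% for bleeds of any size and 94% for extra-axial bleeds above 3.5 ml, so sensitivity depends on which bleeds are included. Specificity was 96% in both of those analyses. It could still shift if CT uptake follows scalp injury or swelling, whose effect on the device the plan lists as an exploratory question.

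The stakes follow from Aim 2. The results are meant to support a later trial of the device where CT cannot be had, and patients without CT are the ones this study leaves unverified.

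**Working it through.** **1. The plan's own figures**

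The half-width is 1.645 × √(0.25/n).

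- n = 68 CT-positive: 0.0997 (plan: 0.099)
- n = 272 CT-negative: 0.0499 (plan: 0.05)
- With CT: 68/0.20 = 340
- All participants: 340/0.50 = 680; allowing 5% dropout, 680/0.95 = 716 (plan: 720)
- Retained: 720 × 0.95 = 684, of whom 342 have CT and 342 do not

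The sizing reproduces to within rounding. Half of the retained participants are unverified by design.

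**2. When CT-only sensitivity is biased**

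It is biased only if, among patients with a hematoma, CT uptake and device sensitivity vary with the same factor.

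Illustration. All inputs except the 50% uptake are assumptions, set so that overall prevalence matches the plan's 20%. Half of patients are severe (prevalence 0.30, sensitivity 0.94) and half mild (prevalence 0.10, sensitivity 0.70). Overall CT uptake is 50%.

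- True prevalence: 0.5 × 0.30 + 0.5 × 0.10 = 0.20
- True sensitivity: (0.15 × 0.94 + 0.05 × 0.70)/0.20 = 0.88

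If a share w of the CT patients is severe, CT-only prevalence is 0.30w + 0.10(1 − w), and CT-only sensitivity is [0.30w × 0.94 + 0.10(1 − w) × 0.70] divided by that prevalence.

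| CT uptake, severe/mild | w | CT-only prevalence | CT-only sensitivity |
|---|---|---|---|
| 40%/60% | 0.4 | 0.18 | 0.1548/0.18 = 0.86 |
| 50%/50% | 0.5 | 0.20 | 0.88 (no bias) |
| 60%/40% | 0.6 | 0.22 | 0.1972/0.22 = 0.90 |
| 70%/30% | 0.7 | 0.24 | 0.2184/0.24 = 0.91 |
| 80%/20% | 0.8 | 0.26 | 0.2396/0.26 = 0.92 |

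For scale, the 90% half-width at sensitivity 0.88 with 68 positives is 1.645 × √(0.88 × 0.12/68) = 0.065.

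**3. A second illustration, starting from the CT group**

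Take CT patients at prevalence 0.20 and sensitivity 0.86 (the earlier series), and assume prevalence 0.10 without CT. With sensitivity s in the no-CT half, overall sensitivity is (0.5 × 0.20 × 0.86 + 0.5 × 0.10 × s)/0.15.

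- s = 0.50: 0.74
- s = 0.70: 0.81
- s = 0.86: 0.86
- s = 0.94: 0.89

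The CT-only 0.86 is then off by +0.12 to −0.03. Only the harshest assumption exceeds the planned ±0.10.

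**4. Predictive values**

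Hold sensitivity at 0.86 and specificity at 0.96. PPV in CT patients at prevalence 0.20 is 0.172/(0.172 + 0.032) = 0.84.

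- No-CT prevalence 0.02: overall prevalence 0.11, PPV 0.0946/(0.0946 + 0.0356) = 0.73
- No-CT prevalence 0.30: overall prevalence 0.25, PPV 0.215/(0.215 + 0.030) = 0.88

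The planned table over a range of prevalences can display this movement. It cannot show a change in sensitivity or specificity.

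**5. The interim input**

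Section 14(c) divides 68 by the prevalence to get the number of patients *with CT*. Prevalence among the 150 CT-scanned interim patients is exactly that quantity, so it is the right input for re-estimation as it stands.

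**The case against.** The case against this point has real weight.

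- **Blinding.** The classical form of verification bias, in which the index test decides who is verified, is removed. This stands. Only indirect selection remains, and a correction using the device result alone, without covariates, would change little.
- **The definitions already point to CT.** Section 14(b) ties sensitivity and specificity to CT, and Section 14(c) counts CT-proven positives and CT negatives. A reader might infer that patients without CT will enter the accuracy tables under a second reference standard. No section says so, and the definitions point the other way. What stands is that the plan never excludes them explicitly and does not say what their analysis is.
- **PPV and NPV are partly covered** by the planned range of prevalences. This stands.
- **The 50% may be too low.** CT criteria are required for entry and the study pays for some scans. This is a fair challenge to the premise, but the trial is sized on 50% and the two provisions are not reconciled.
- **Direction and size are assumed.** A reader might infer that CT-only figures overstate sensitivity because sicker patients are scanned more often. The documents attribute missing CT to cost, breakdown and access, and early death ends data collection, so the effect could be nil or reversed. In the first illustration even the 80%/20% split moves sensitivity by 0.04, inside the 0.065 half-width.
- **The interim decision.** A reader might also infer that re-estimating the sample size inherits the bias. It does not, as step 5 shows. Only the description of that prevalence as applying to the hospital is too broad.

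**Conclusion.** The point holds as a mismatch between the population in the objective and the population in which accuracy can be estimated, left unaddressed by an undefined analysis of the unverified half. CT-only sensitivity, specificity and prevalence may misstate the values for all hospitalised head-trauma patients.

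The amount rests wholly on assumptions. It is +0.02 to +0.04 in sensitivity with severity-driven uptake in the first illustration, −0.02 with the mild reverse pattern, and +0.12 to −0.03 in the second. It is zero if CT uptake is unrelated to hematoma presence and device accuracy, and negligible if nearly everyone is scanned. No figure was derived for specificity, because the documents give nothing to vary it by.

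The change is worth making before analysis, since it decides what the primary result can be said to describe. The sample-size arithmetic and the interim re-estimation are not faulted here. The charts in Sections 5 and 8 are not visible in the text available, so any detail given only there could not be checked.

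**What to change.** 1. State in Section 14(b) that patients without CT enter no sensitivity, specificity or predictive-value table, in line with that section's definitions. Define their analysis as descriptive, or drop it.
2. Report baseline clinical data (for example severity, age and time since injury) and device-positive rates by CT status.
3. Add one sensitivity analysis that reweights CT-verified patients by the inverse probability of CT given recorded baseline covariates, or a covariate-stratified Begg-Greenes correction. State that it removes bias only through recorded variables.
4. Word the primary conclusions for CT-verified patients. Label the interim prevalence as that among CT-scanned patients, and keep it unweighted for sample-size re-estimation.
5. Reconcile the study-paid CT provision in Section 14(a) with the 50% assumption in Section 14(c), and say what share is expected to remain without CT.
6. Add incomplete verification to Section 17.

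The cost is SAP wording, one table and one extra analysis with somewhat wider intervals. The planned total of 720 is unaffected by items 1 to 4; item 5 could change it if the expected CT share changes. Section 14(b) presupposes clinical data on patients without CT, but which variables are recorded could not be confirmed. If severity is not among them, it would need to be added for item 3 to be useful.

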A few years ago, the InfraScanner 2000TMwas introduced, prompting our group to validate it in a consecutive series of 500 head injury patients who obtained a head CT scan at Duke University Hospital (DUH). For all patients with CT-proven bleeds (n=104), irrespective of size, initial NIRD scans localized the bleed to the appropriate quadrant with a sensitivity of 86% and specificity of 96% compared to CT scan. For extra-axial bleeds >3.5ml, sensitivity and specificity were 94% and 96%, respectively. For longitudinal serial rescans with the NIRD, sensitivity was 89% (<4 days from injury: sensitivity=99%) and specificity was 96%. For all patients who required craniectomy or craniotomy, the device demonstrated 100% sensitivity.

Infrascanner Study PI: [name]

With these results, the Duke Global Neurosurgery and Neurology (DGNN) proposes to initiate a trial to replicate our DUH findings at MRRH: using the Infrascanner 2000TM in the background of the current standard of care to quantify the accuracy of the device – the positive and negative predictive values – in diagnosing SDH/EDH relative to CT in the Ugandan setting.

We hope that, with positive results, this work can lay the foundation for a subsequent trial using the device to diagnose intracranial bleeds when CT scans cannot be accessed in a timely manner. Such a result could ostensibly improve neurocritical and neurosurgical care in Uganda when obtainment of a CT scan is not feasible in a rapidly deteriorating patient.

As the sensitivity and specificity in detecting traumatic intracranial hematomas approaches that of CT scanning, the prospect of using the InfraScanner 2000TM as a stand-alone diagnostic device for intracranial hematomas in low-resource settings that lack CT scans is highly intriguing. In geographical locations where TBI burden is highest and need for emergency craniotomies is most pressing, the inability to obtain CT scans precludes hundreds to thousands of life-saving surgeries everyday. The use of a handheld device that can be used repeatedly to reliably diagnose and track intracranial bleeding at no cost to a patient could revolutionize the prognosis of TBI for the majority of the 10 million people it affects annually.

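### The only interval formula in the plan (Wald, section 14(c)) is modestly too optimistic about sensitivity if it is used for reporting; a Wilson interval should be named for the analysis, with no change in sample size

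*Combined protocol and SAP*

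**What the plan says.** The primary objective in section 14 is estimation of test characteristics against CT, for hematomas of any size. The secondary objective repeats this for hematomas within the device's detection limits (more than 3.5 mL, less than 2.5 cm deep). There is no hypothesis test, so intervals are the main inferential output.

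Section 14(c) bases the size on "estimating the sensitivity of each method to within at most" 0.10 with 90% confidence. It continues: "The 90% confidence interval for the sensitivity is given by" P ± 1.645·SE(P), with SE built from P(1 − P)/N. It adds that "N denotes the number of true positives", by which it means CT-positive patients. Then: "With 68 patients with positive findings of hematoma", "sensitivity can be estimated to within at most +/- 0.099 with 90% confidence". The accrual follows: "Assuming 20% of patients have true hematomas detected, 340 patients who obtain CT scans must be accrued". For the 272 CT-negative patients, "specificity can be estimated to within at most +/- 0.05 with 90% confidence".

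Section 14(d) plans an interim look at 150 patients with CT and announces an adjusted 90% interval for sensitivity, without saying how it is adjusted or built. No other interval method is named.

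The results to be replicated are in section 3: 86% sensitivity and 96% specificity for bleeds of any size, and "For extra-axial bleeds >3.5ml, sensitivity and specificity were 94% and 96%, respectively".

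**The concern.** The Wald interval takes its width from the estimate itself. As the estimate nears 1 the standard error shrinks towards zero, so the lower limit sits too high, the upper limit can pass 100%, and with no misses the interval has zero width. The protocol expects accuracy in this region with small denominators: 68 CT-positive patients in the primary analysis, 150 × 0.20 = 30 at the interim, and fewer than 68 in the within-limits analysis.

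The direction matters. Aim 2 uses the findings to inform a future trial of stand-alone use where CT is unavailable. A lower limit that is too high understates how many bleeds the device could miss. This holds for independent patient-level data and is separate from any correlation between repeat scans of one patient.

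**Working it through.** **1. Reproduce the plan's figures (Wald, worst case P = 0.5).**
- 1.645 × √(0.25/68) = 0.0997, stated as 0.099.
- 68/0.20 = 340; 340/0.50 = 680; 680/0.95 = 716, rounded to 720.
- 1.645 × √(0.25/272) = 0.0499, stated as 0.05.

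The figures reproduce only with a square root in the SE. Its absence from the text as read is not treated as an error.

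**2. Inputs for the check.** Sensitivity 0.86 (any size, section 3) and 0.94 (more than 3.5 mL, section 3); specificity 0.96; prevalence 20% and 340 patients with CT (14(c)); interim at 150 patients with CT (14(d)). The plan accrues patients, not hematomas, so the number of CT-positives N is random.

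**3. Method.** For each N, sum the binomial probabilities of the outcomes x whose interval contains the true value, lies wholly above it (lower limit too high) or lies wholly below it. Then average over N. The Wilson limits are

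[p + z²/(2N) ± z√(p(1 − p)/N + z²/(4N²))] / (1 + z²/N), with p = x/N and z = 1.645.

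**4. Results for 90% intervals.**

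| Setting | True value | Wald coverage | Wald lower limit too high | Wald upper limit > 100% | Wald zero width | Wilson coverage | Wilson lower limit too high |
|---|---|---|---|---|---|---|---|
| Primary, N ~ Bin(340, 0.20) | 0.86 | 88.0% | 8.9% | 0.4% | 0.01% | 90.1% | 4.2% |
| Same | 0.94 | 86.4% | 11.7% | 20.8% | 1.7% | 90.8% | 3.0% |
| Specificity, N ~ Bin(340, 0.80) | 0.96 | 88.9% | 8.4% | – | – | 90.4% | 3.9% |

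Other settings:
- **Exactly N = 68.** Wald coverage is 90.4% at 0.86 and 90.0% at 0.94; the lower limit is too high in 7.2% and 8.0%. Coverage moves in steps. Over all true values from 0.86 to 0.94 at N = 68 it averages 87.1% (range 78.5% to 92.0%), and the lower-limit error averages 10.3% and never falls below 6.0%.
- **Secondary, true value 0.94, assuming 50-75% of hematomas are within limits** (N ~ Bin(340, 0.10) to Bin(340, 0.15)). Wald coverage is 82-85%, lower limit too high in 14-16%, upper limit above 100% in 36-54%, zero width in 5-13%.
- **Interim, N ~ Bin(150, 0.20), if the unadjusted formula were used.** At 0.86 and 0.94, coverage is 86.1% and 82.3%; upper limit above 100% in 19% and 57%; zero width in 1.4% and 16%.
- **Other prevalences in 340 patients.** From 10% to 50%, Wald coverage at 0.86 runs from 86.4% to 89.3%.

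**5. Worked examples.**
- 58/68 = 0.853: Wald 0.853 ± 1.645 × √(0.853 × 0.147/68) = 0.782 to 0.924; Wilson 0.769 to 0.910.
- 64/68: Wald 0.894 to 0.988; Wilson 0.875 to 0.973.
- 66/68: the Wald upper limit is 1.004.
- 68/68: Wald 1.000 to 1.000; Wilson 68/(68 + 1.645²) = 0.962 to 1.000.

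**6. Effect of the alternative on planning.** The worst-case Wilson half-width is 0.098 at N = 68 and 0.0496 at N = 272, so the stated precision is kept.

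**The case against.** The strongest reply is that the formula is a planning formula. It sits under the sample-size heading and is applied at P = 0.5, where the normal approximation is adequate. This stands in part: the text does not expressly adopt Wald for the final report. But the wording is general and nothing replaces it, so an analyst following the plan would have no other formula to use.

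Several stronger readings are tempting and are not supported:
- *Wald simply fails to give 90% here.* At exactly 68 positives and a sensitivity of 86% or 94% it covers 90.4% or 90.0%. The shortfall appears once N, or the true sensitivity, is allowed to vary. At the primary 86% it is about 2 points.
- *The primary result is likely to be unreportable.* At 86%, limits above 100% and zero width occur in 0.4% and 0.01% of trials.
- *The interim interval is Wald.* Section 14(d) calls it adjusted and gives no form, so the interim figures above are conditional.
- *A decision turns on the lower limit.* No threshold or success rule is tied to it, and stand-alone use is left to a future trial. The 5% per tail is implied by a symmetric 90% interval, not stated.

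It is also fair that Wilson is not perfectly balanced: its upper limit falls below the truth in about 6% of trials in these settings. An exact interval would also cure the defects.

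**Conclusion.** The point holds as a modest, one-directional weakness in the only interval formula given, conditional on that formula being used for reporting. With N ~ Bin(340, 0.20), Wald coverage is about 88% at 86% and 86% at 94%. The lower limit is too high in about 9-12% of trials, which is 1.8 to 2.3 times the implied 5% (1.4 to 1.6 times at exactly 68 positives). Overshoot and zero width matter near 94% with fewer positives, chiefly in the secondary analysis.

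This rests on independent patients, the plan's 20% prevalence, and sensitivities close to those in section 3. The secondary figures also rest on an assumed 50-75% share of hematomas within limits, which the documents do not give. A reader might infer that the sample size is wrong; it is not, since every planning figure reproduces.

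**What to change.** Leave the sample-size figures in 14(c) as they are. Add one sentence to section 14: patient-level sensitivity and specificity will be reported with 90% Wilson score intervals in the primary and secondary analyses, and the Wilson interval will be the base for the adjusted interim interval in 14(d), whose adjustment should be stated. A Clopper-Pearson exact interval is an acceptable, more conservative alternative. Its coverage is 93.1% at 0.86 and 94.8% at 0.94 in the primary setting, but its worst-case half-width of about 0.106 at 68 positives is slightly beyond the 0.10 target. Scan-level estimates need a method that allows for repeat scans; this sentence does not cover them.

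The cost is one sentence and one software option, with no extra patients or procedures. The downside is slightly less favourable lower limits: about 1.3 points at 58/68 (0.782 to 0.769), 1.9 points at 64/68 (0.894 to 0.875) and 3.8 points at 68/68 (1.000 to 0.962). For specificity the change is about 0.5 points at 261/272 (0.940 to 0.935).
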